**13.5.2 Reporting to karyopharm**

In addition to reporting to the FDA, Sponsor-Investigator will forward completed SAE and pregnancy forms to representatives of karyopharm. Forms will be completed and emailed to [REDACTED]

Address and Phone Number of person/sponsor responsible for SAE management

[REDACTED]  
[REDACTED]  
[REDACTED]  
[REDACTED]

IN ADDITION, scanned form must be emailed to the following recipients:

[REDACTED]  
[REDACTED]  
[REDACTED]

The Sponsor / investigator is responsible for providing 6-month Adverse Reaction Reports (all AEs assessed as causality related to Karyopharm investigational product) to Karyopharm [REDACTED] throughout the duration of the study. These reports are to contain listings of non-serious (expected or unexpected) adverse reactions and serious or non-serious expected adverse reactions which were collected during the 6-month report cycle

*The Sponsor is responsible for obtaining any additional follow-up information regarding safety reports, upon request from Karyopharm.*

*Karyopharm will inform the Sponsor regarding any SUSAR detected in other clinical studies, ISTs, or Compassionate Use as promptly as possible upon becoming aware of same*

### **13.5.3 Reporting to the IRB**

The principal Investigator is required to notify his/her Institutional Review Board (IRB) of a serious adverse event according to institutional policy. The following SAE are reported to the IRB: Unexpected, related events which increase the risk of harm to subjects.

### **13.6 Adverse Events Updates / IND Safety Reports**

Karyopharm Therapeutics shall notify the Investigator via an IND Safety Report of the following information:

- Any AE associated with the use of study drug in this study or in other studies that is both serious and unexpected.
- Any finding from tests in laboratory animals that suggests a significant risk for human subjects including reports of mutagenicity, teratogenicity, or carcinogenicity.

The Investigator shall notify his/her IRB/EC promptly of these new serious and unexpected AE(s) or significant risks to subjects.

## **14 DATA MANAGEMENT**

### **14.1 Data Collection**

The Clinical Research Coordinators and Investigators of each site will be responsible for the recording of the site's data into the electronic data capture system, ONCORE.

To obtain access to Oncore, the site research staff must complete an Oncore Access Request Form and a Moffitt Information Systems Confidentiality Agreement (provided in the MCRN Handbook at the site initiation visit) and submit both to the Coordinating Center. Once the completed forms are received, the site coordinator will receive VPN access, logon/password, and information on how to access Oncore using the VPN. The MCRN Coordinating Center will provide Oncore training to the site once initial access is granted and on an ongoing basis, as needed.

### **14.2 Protocol Monitoring Committee**

The Protocol monitoring committee (PMC) will be composed of medical and statistical independent reviewers and will meet to review the efficacy and safety data and determine a

risk/benefit analysis in this subject population. The purpose of the PMC is to advise on serious safety considerations, lack of efficacy and any other considerations within the charge to the Committee. The PMC may request additional meetings or safety reports as deemed necessary upon discussion with the principal investigator. The PMC may stop the study following review of results from each interim analysis.

### **14.3 Study Monitoring and Auditing**

#### **14.3.1 Investigator Responsibilities**

Investigator responsibilities are set out in the ICH guideline for Good Clinical Practice (GCP) and in the US Code of Federal Regulations. The principal investigator is responsible for every aspect of the design, conduct and actions of all members of the research team as well as final analysis of the protocol.

Investigators, or a designated member, must enter study data onto CRFs or other data collection system. The Investigator will permit study-related monitoring visits and audits by Karyopharm Therapeutics or its representatives, IRB/EC review, and regulatory inspection(s) (e.g., FDA, EMEA, TPP), providing direct access to the facilities where the study took place, to source documents, to CRFs, and to all other study documents.

The Investigator, or a designated member of the Investigator's staff, must be available at some time during monitoring visits to review data and resolve any queries and to allow direct access to the subject's records (e.g., medical records, office charts, hospital charts, and study related charts) for source data verification. The data collection must be completed prior to each visit and be made available to the Karyopharm Therapeutics representative so that the accuracy and completeness may be checked.

#### **14.3.2 Site Responsibilities**

Before the study can be initiated at any site, the site will be required to provide regulatory documentation to the Moffitt Clinical Research Network (MCRN) at Moffitt Cancer Center.

Sites must provide a copy of their informed consent to the MCRN coordinating center for review and approval prior to submission of any documents to the site's IRB. Any changes requested by the site's IRB must be provided to the MCRN staff for review and approval prior to resubmission to the IRB.

The MCRN Coordinating Center must receive the following trial specific documents either by hardcopy, fax, or email before a site can be activated for any trial:

1. IRB Approval Letter that includes the protocol version and date
2. FDA Related Forms 1572/1571/310 as appropriate
3. Signed Protocol Title Page
4. IRB Approved Consent Form
5. Site Delegation of Authority Log
6. Signed Financial Interest Disclosure Forms (principal and sub investigators)

7. Updated Investigator/Personnel documents (CVs, licenses, Conflict of Interest statements, etc.) as needed
8. Updated Laboratory Documents (certifications, normal ranges, etc.) as needed
9. Signed protocol specific Task Order

A study initiation teleconference will be held prior to the start of any study related activity at the site. Attendance is required for:

- The site PI and appropriate research staff
- Moffitt PI and MCRN research coordinator

The requirements of the protocol and all associated procedures and processes will be reviewed and agreed upon prior to the activation of the study. The MCRN utilizes the EDC system, Oncore. Oncore training will be scheduled, if indicated, with the appropriate staff from the site.

A conference call/study meeting will be held weekly for the phase I and monthly for the phase II to review patient enrollment and accrual, safety and toxicity data, and treatment results, as available.

#### **14.3.3 Monitoring**

Data will be captured in Oncore, Moffitt's Clinical Trials Database. Regulatory documents and case report forms will be monitored internally according to Moffitt Cancer Center Monitoring Policies. Monitoring will be performed regularly to verify data is accurate, complete, and verifiable from source documents; and the conduct of the trial is in compliance with currently approved protocol / amendments, good clinical practice (GCP) and applicable regulatory requirements. Monitoring at external sites will be per Moffitt policy.

## **15 PROTOCOL AMENDMENTS OR DEVIATIONS**

### **15.1 Protocol Amendments**

Any amendment to this protocol must be agreed to by the Principal Investigator and reviewed and approved by Karyopharm Therapeutics. Amendments should only be submitted to IRB/EC after consideration of Karyopharm Therapeutics review. Written verification of IRB/EC approval will be obtained before any amendment is implemented.

### **15.2 Protocol Deviations**

When an emergency occurs that requires a deviation from the protocol for a subject, a deviation will be made only for that subject. A decision will be made as soon as possible to determine whether or not the subject (for whom the deviation from protocol was effected) is to continue in the study. The subject's medical records will completely describe the deviation from the protocol and state the reasons for such deviation. In addition, the Investigator will notify the IRB/EC in writing of such deviation from protocol.

### APPENDIX A: Response Criteria

Response Category	Response Criteria a
Stringent CR (sCR)	CR as defined below plus 1. Normal free light chain (FLC) ration and 2. Absence of clonal cells in bone marrow b by immunohistochemistry or immunofluorescence c
Complete Remission (CR)	Negative immunofixation on the serum and urine and disappearance of any soft tissue plasmacytomas and $\leq 5\%$ plasma cells in bone marrow b
Very Good Partial Remission (VGPR)	Serum and urine M-protein detectable by immunofixation but not on electrophoresis or 90% or greater reduction in serum M-protein plus urine M-protein level $< 100$ mg per 24 hours In patients with only FLC disease, $>90\%$ decrease in the difference between involved and uninvolved FLC levels is required.
Partial Remission (PR)	$\geq 50\%$ reduction of serum M-Protein and reduction in 24-hour urinary M-protein by $\geq 90\%$ or to $< 200$ mg per 24 hours If the serum and urine M-protein are unmeasurable d a $\geq 50\%$ decrease in the difference between involved and uninvolved FLC levels is required in place of the M-protein criteria In addition to the above, if present at baseline a $\geq 50\%$ reduction in the size of soft tissue plasmacytomas is also required
Minimal Remission (MR)	25-49% reduction in serum paraprotein and a 50-89% reduction in urine light chain excretion. A 25-49% reduction in the size of soft tissue plasmacytoma must be demonstrated is applicable
Stable Disease (SD) e	Not meeting criteria for CR, VGPR, PR, or progressive disease
Progressive disease (PD) f	Requires only one of the following: Increase of $\geq 25\%$ from baseline in: 
 
 Serum M-component and/or (the absolute increase must be <math>\geq 0.5</math> g/dl)g
 
 Urine M-component and/or (the absolute increase must be <math>\geq 200</math> mg/24 hours)
 
 the difference between involved and uninvolved sFLC levels (In patients without measurable serum and urine M-protein levels), the absolute increase must be <math>> 10</math> mg/dl.
 
 the size of existing bone lesions or soft tissue plasmacytomas as well as definite development of new bone lesions or soft tissue plasmacytomas
 
 Development of hypercalcemia (corrected serum calcium <math>> 11.5</math> mg/dl) that can be attributed solely to the plasma cell disorder.
 

a. All response categories require two consecutive assessments made at anytime before the institution of any new therapy; all categories also require no known evidence of progressive or new bone lesions if radiographic studies were performed. Radiographic studies are not required to satisfy these response criteria.

b Confirmation with repeat biopsy not necessary.

c Presence/absence of clonal cells is based upon the  $\kappa/\lambda$  ratio by immunohistochemistry and/or immunofluorescence requires a minimum of 100 plasma cells for analysis. An abnormal ration reflecting presence of an abnormal clone is  $\kappa/\lambda$  of  $> 4:1$  or  $< 1:2$ .

d Applicable only to patients who have 'measurable' disease defined by at least one of the following three measurements: Serum M-protein  $\geq 0.5$  g/dl, Urine M-protein  $\geq 200$  mg/24hour, Serum FLC assay involved FLC level  $\geq 10$  mg/dl provided serum FLC ration is abnormal. e. Not recommended for use as an indicator of response; stability of disease is best described by providing the time to progression estimates).

f All relapse categories require two consecutive assessments made at anytime before classification as relapse or disease progression and/or the institution of any new therapy.

g For progressive disease, serum M-component increases of  $\geq 1$  g/dL are sufficient to define relapse if starting M component is  $\geq 5$  g/dL. Progression can also be defined by a 25% increase in the serum M component or M spike provided that the increase is  $>0.5$  g/dL.

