
Treatment and Post-Treatment Assessments
	
Loading Phase  Physical examination and vital signs (includes weight and ECOG performance status) (on day -7 only)  Hematology (on day -7 only)  Clinical chemistry (on day -7 only)  Assessment of disease status (Day -7) (SPEP, 24h UPEP, serum free light chain)  PK of selinexor (appendix C)  Adverse events and concomitant medication  Pregnancy test (if applicable)  Bone Marrow aspiration and biopsy at least 2 hours post selinexor dosing on day -7
 
Cycle 1  Physical examination and vital signs (includes weight and ECOG performance status)  Hematology  Complete clinical chemistry (weekly in cycle 1)  Assessment of disease status (SPEP, 24h UPEP, serum free light chain)  PK of doxorubicin, and selinexor and PD (appendix C)  Adverse events and concomitant medication  Pregnancy test (if applicable)
 
Cycle 2 and Beyond  Physical examination and vital signs (on day 1) (includes weight and ECOG performance status)  Cardiac evaluation (echocardiogram or MUGA every 2 cycles if patient has prior anthracycline exposure with greater than 450 mg/m^2)  Hematology (on day 1)  Complete clinical chemistry (on day 1)  Assessment of disease status (SPEP, 24h UPEP, serum free light chain) (on day 1)  Adverse events and concomitant medication  Pregnancy test (if applicable)  PK of doxorubicin, and elinexor and PD (appendix C)
 
Final Visit (end of study)  Physical examination and vital signs (includes weight and ECOG performance status)  Pregnancy test (if applicable)  Cardiac evaluation (echocardiogram or MUGA)  Hematology

--	--

	
Complete clinical chemistry
 
Assessment of disease status (SPEP, 24h UPEP, serum free light chain)
 
Bone marrow aspiration and biopsy (in the event of discontinuation due to disease progression)
 
Adverse events and concomitant medication
 
Pregnancy test (if applicable)

Response	
Response will be assessed per the uniform response criteria of the IMWG incorporating minimal response (<math>\geq 25\%</math> decrease in serum M protein and <math>\geq 50\%</math> decrease in the 24h urine m spike).

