### **1.5.4 Assessment for Response**

The uniform response criteria of the international myeloma working group (IMWG) will be used for response assessment (see Appendix A) [47].

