### **6.1 Study Assessments**

#### **6.1.1 Efficacy Assessments**

The clinical activity of selinexor will be evaluated for its effects on disease response criteria in terms of best response, duration of response, progression-free survival (PFS) and overall survival (OS). Disease status will be measured by the uniform response assessment of the International Myeloma Working Group.

The baseline disease assessment must be recorded and measured within 28 days prior to treatment start. During the treatment period, disease assessments will be performed every cycle, and as clinically indicated.

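### Appendix A caps every component of minimal response, so a stronger mixed responder can fall to stable disease while a weaker one counts as MR; the synopsis rule has no caps and no plasmacytoma term

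*Combined protocol and SAP*

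**What the plan says.** Section 1.5.4 states that the IMWG uniform criteria "will be used for response assessment (see Appendix A").

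Appendix A gives these rules:
- **MR:** "25-49% reduction in serum paraprotein and a 50-89% reduction in urine light chain excretion". For plasmacytoma: "A 25-49% reduction in the size of soft tissue plasmacytoma must be demonstrated is applicable".
- **PR:** at least a 50% "reduction of serum M-Protein and reduction in 24-hour urinary M-protein by" at least 90%, or to under 200 mg/24 h. If plasmacytomas were present at baseline, they must also shrink by at least 50%.
- **SD:** "Not meeting criteria for CR, VGPR, PR, or progressive disease".
- **Footnote a:** "All response categories require two consecutive assessments made at anytime before the institution of any new therapy".

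The Response row of the synopsis describes minimal response differently, as at least a 25% "decrease in serum M protein and \geq 50\% decrease in the 24h urine m spike". It sets no upper limits and does not mention plasmacytoma.

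The clinical benefit rate (MR or better) is a secondary objective in section 2.2 and a secondary endpoint in section 11.1.2. Section 6.1.1 says that activity will be "evaluated for its effects on disease response criteria in terms of best response", among other measures.

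**The concern.** Response categories should be ordered: improving one component and changing nothing else should never lower a patient's category. Appendix A breaks this order. Its MR ceilings sit where the PR thresholds begin, which works only if all components move together. In a mixed response, one component can pass its MR ceiling while another stays short of PR, and then neither category applies.

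At stake is the clinical benefit rate, because MR is the category that separates it from the overall response rate. Under Appendix A as written the rate could omit some patients with deeper mixed responses and count patients with shallower ones. An analyst who programmed the synopsis line instead could obtain a different rate from the same data.

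**Working it through.** **Inputs.** These are the PR, MR and SD rows of Appendix A and the synopsis Response row. The documents state no figure that depends on MR, so there is none to reproduce. The check applies each rule literally to the same patients, best category first.

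**Classification.** Baseline urine M-protein is assumed to be 2,000 mg/24 h, so a 70% fall leaves 600 mg and a 95% fall leaves 100 mg. The last column uses the single rule proposed under the fix.

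| Case | Serum fall | Urine fall | Plasmacytoma fall | Appendix A | Synopsis | Single rule |
|---|---|---|---|---|---|---|
| A | 40% | 70% | none present | MR | MR | MR |
| B | 40% | 95% | none present | SD | MR | MR |
| C | 60% | 70% | none present | SD | MR | MR |
| D | 40% | 70% | 30% | MR | MR | MR |
| E | 40% | 70% | 60% | SD | MR | MR |
| F | 40% | 70% | 10% | SD | MR | SD |

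- B is at least as good as A on every component but ranks lower. Urine exceeds 89%, so it is not MR; serum is under 50%, so it is not PR.
- C also ranks below A. Serum exceeds 49%, so it is not MR; the urine fall is under 90% with at least 200 mg/24 h left, so it is not PR.
- E ranks below D only because the plasmacytoma shrank more.
- F shows the separate mismatch over plasmacytoma: the synopsis ignores it and Appendix A does not.

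**Dependence on baseline.** Case C needs a baseline of at least 200/(1 - 0.70) = 667 mg/24 h. From 500 mg/24 h, a 70% fall leaves 150 mg and the patient is PR.

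**Extent of the gap in the rules.** Take whole-percent falls from 0 to 100 and no plasmacytoma. The synopsis floors cover 76 x 51 = 3,876 serum-urine pairs, and Appendix A MR covers 25 x 40 = 1,000.
- Baseline 2,000 mg/24 h: PR takes 51 x 11 = 561, leaving 3,876 - 561 - 1,000 = 2,315 pairs that are SD in Appendix A and MR in the synopsis.
- Baseline 500 mg/24 h: PR takes 51 x 40 = 2,040, leaving 836.

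These counts describe the rules. They are not patient frequencies.

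**Direction of the fix.** Every Appendix A MR patient meets the floors, and a serum fall of at most 49% rules out PR. If progression overrides under either rule, the single rule can therefore only add patients relative to Appendix A. Relative to the synopsis it adds a requirement, so it can only remove them, as in case F.

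**Size per patient.** The documents state no denominator for this rate. Assumed values are 47 (maximum enrolment), 29 (full phase II set) and 13 (stage 1 only): 1/47 = 2.1 points, 1/29 = 3.4 points, 1/13 = 7.7 points. For scale, at an assumed rate of 50% in 29 patients the approximate 95% half-width is 1.96 x sqrt(0.25/29) = 18.2 points, so one patient is 3.4/18.2 = 0.19 of it.

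**The case against.** The strongest reply is that the bands form a ladder: the ceilings only mark where PR takes over, and nobody would downgrade a deeper response. The floor-only synopsis supports that intention. In addition, the SD row does not list MR among its exclusions, so on a fully literal reading every MR patient is also SD, and the inversion relies on taking the best category first.

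The dependence on best category first is conceded. The ladder reading is plausible as intent, but it replaces the wording of the appendix that section 1.5.4 names as the source. It also leaves the plasmacytoma disagreement with the synopsis unresolved.

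The limits on reach stand in full. A patient needs more than one assessable component, and must never have two consecutive assessments that qualify as MR or better. The documents set no test or target for the rate, and section 11.6 does not name it among the secondary endpoints to be analysed. Maintenance is open to patients with stable disease or better, so treatment does not depend on the MR label.

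A reader might infer that the reported clinical benefit rate will be materially too low, or that the efficacy decision is compromised. The documents support neither. They give no distribution of baseline urine protein, plasmacytoma or mixed response from which to estimate a frequency. The primary endpoint uses PR or better, which does not refer to MR.

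**Conclusion.** The point holds as a definitional error of low consequence. Appendix A ranks some stronger mixed responses below weaker ones, and it conflicts with the synopsis on both the caps and plasmacytoma. The conclusion rests on a literal reading with the best category assigned first.

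Only the clinical benefit rate and the best-response table are exposed. The overall response rate and the Simon limits (3 of 13, 8 of 29) are unaffected. The number of patients affected cannot be derived from the documents and may be zero; the effect per patient depends on which denominator is adopted. The synopsis line should not be taken as the correct version either, because it would count a patient whose plasmacytoma has barely changed.

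**What to change.** Put one MR rule in both the synopsis and Appendix A:
- serum reduction of at least 25% and urine reduction of at least 50%;
- plasmacytoma reduction of at least 25% if present at baseline;
- not meeting PR or better (PR, VGPR, CR, sCR) or progressive disease.

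List MR among the categories excluded from SD. The exclusion must read PR or better because the VGPR row has no plasmacytoma term: serum down 95%, urine under 100 mg/24 h after a fall of at least 50%, and plasmacytoma down 30% meets VGPR, fails PR, and would otherwise also meet MR.

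Date and justify the change, state the denominator, and report the clinical benefit rate under the current Appendix A wording and the current synopsis wording as sensitivity analyses. Both are needed because the new rule can raise the rate against the first and lower it against the second. The trial is open-label and single-arm, section 1.5.2 already names dose level 2m as the recommended phase II dose, and six phase I patients treated at that dose count in stage 1, so an undated change could look data-driven.

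The cost is wording in two places, one derivation rule and two sensitivity lines. Serum, urine and free light chain are already measured on day 1 of every cycle and plasmacytomas every two cycles, so no visits or patients are added. How MR applies to patients measurable in only one of serum, urine or free light chain is a separate clarification and not part of this error.

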### **11.6 Analysis of the Phase II**

For the primary endpoint in Phase II trial, we are interested in comparing the overall response rate of this combination with historical efficacy data using liposomal doxorubicin and dexamethasone in patients with relapsed and refractory myeloma. The overall response rate and its 95% confidence will be calculated using the method proposed by Atkinson and Brown[49]. This confidence interval takes into account the nature of the two-stage Simon design.

The secondary endpoints include progression-free survival (PFS), overall survival (OS), safety, and duration of response. Patients will be followed for survival and progression until termination of the study. PFS is defined as the time from start of treatment to death of any cause, disease progression, or the date of last follow-up, whichever comes first. OS is defined as the time from start of treatment to death of any cause or the date of last follow-up, whichever comes first. The time-to-event data will be estimated using the Kaplan-Meier method. The median of PFS and OS and 95% confidence intervals will be computed. The effect on time-to-event data adjusting for other factors (such as age and tumor stage) will be analyzed using the Cox proportional hazards regression models.

As the exploratory endpoints, the association between the change of each biomarker (e.g., nucleus to cytoplasm ratio, p53, CRM1, I $\kappa$ B and NF $\kappa$ B) from screening to day 1 of cycle 1 and the response to the therapy will be examined by the Satterthwaite t-test or the Wilcoxon rank sum test. The appropriate transformation such as log-transformation may be considered if necessary. In addition, we will examine if the disease progression is associated with the change from screening to date of progression or from day 1 of cycle 1 to date of progression. No multiplicity adjustment is planned due to the nature of exploratory study. A two-sided p-value of < 0.05 will be considered significant. We expect that 12 or more of 29 patients in Phase II are responders. With a two-sided significance level of 5%, 29 samples will provide 80.4% power to detect an effect size (mean difference divided by standard deviation) of 1.2 when the numbers of responders and non-responders are 12 and 17, respectively.

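### Progression is measured from the pre-treatment baseline (for serum, from an unclear reference), so after a marker fall PFS events are dated later, or for serum inconsistently, relative to a lowest-value rule

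*Combined protocol and SAP*

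**What the plan says.** The progressive-disease row of Appendix A opens "Requires only one of the following: Increase of $\geq 25\%$ from baseline in" and then lists serum M-component, urine M-component, the FLC difference and lesions. The absolute minimum rise is 0.5 g/dL for serum and 200 mg/24 h for urine. The FLC entry is restricted: "the difference between involved and uninvolved sFLC levels (In patients without measurable serum and urine M-protein levels), the absolute increase must be" more than 10 mg/dL. The lesion entry is "the size of existing bone lesions or soft tissue plasmacytomas as well as definite development of new bone lesions or soft tissue plasmacytomas", with no absolute minimum. New lesions and hypercalcemia count without any reference value.

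Section 6.1.1 settles what baseline means: "The baseline disease assessment must be recorded and measured within 28 days prior to treatment start".

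Footnote g modifies the serum entry. Rises of at least 1 g/dL "are sufficient to define relapse if starting M component is" 5 g/dL or more. It then adds: "Progression can also be defined by a 25% increase in the serum M component or M spike provided that the increase is" above 0.5 g/dL. Neither sentence says from which value the rise is counted, and the starting value is not defined.

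Section 11.6 states: "PFS is defined as the time from start of treatment to death of any cause, disease progression, or the date of last follow-up", whichever is earliest. It offers no other definition of progression. It also states: "The secondary endpoints include progression-free survival (PFS), overall survival (OS), safety, and duration of response", and gives duration of response no start or end. No section names a lowest value or best response as the reference, and Appendix A has no separate row for relapse from complete response.

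**The concern.** A patient who responds and then relapses has to regain the whole fall, and then exceed the entry level, before a marker counts as progression. On that reading the effect has one direction: it lengthens PFS in patients who improved, and by more after a deeper fall. It would act on duration of response in the same way if that endpoint ends at progression.

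Serum raises a second problem. Two assessors who both follow Appendix A can date the same serum relapse differently, because footnote g does not say whether its rise is counted from baseline or from the lowest value. The trial runs at three centres, and nothing tells them which reading to use.

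At stake is a secondary endpoint: Section 11.6 reports median PFS with a confidence interval from a single arm, so no concurrent control shares the effect.

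**Working it through.** **Plan figures.** The plan gives no PFS median, event count or power, so there is no PFS figure to reproduce. The Simon figures do reproduce: with 13 then 29 patients, continuing at 3 or more responses and declaring activity at 8 or more, the exact binomial gives power 0.9069 at a 40% response rate (stated 90.7%), early stopping 0.0579 (stated 0.058) and type I error 0.0500 at 15% (stated 0.05). They rest on response only and do not depend on this point.

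**Rule.** For reference value x, the progression threshold is:
- urine: max(1.25x, x + 200) mg/24 h
- FLC difference: max(1.25x, x + 10) mg/dL
- existing lesion: 1.25x
- serum: max(1.25x, x + 0.5) g/dL, capped at x + 1.0 if baseline is at least 5 g/dL (footnote g)

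Delay in doublings = log2(threshold with x = baseline ÷ threshold with x = lowest value), assuming exponential regrowth.

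**Inputs.** The minimum rises come from Appendix A. Falls of 50% and 90% are reductions used in its response rows. The lower urine and FLC examples sit at or near the measurable-disease limits; all other marker levels are assumptions.

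| Marker, baseline | Fall | Threshold from baseline | Threshold from lowest | Doublings |
|---|---|---|---|---|
| Urine 200 mg/24 h | 50% | 400 | 300 | 0.42 |
| Urine 200 | 90% | 400 | 220 | 0.86 |
| Urine 1000 | 50% | 1250 | 700 | 0.84 |
| Urine 1000 | 90% | 1250 | 300 | 2.06 |
| FLC difference 10 mg/dL | 50% | 20 | 15 | 0.42 |
| FLC difference 10 | 90% | 20 | 11 | 0.86 |
| FLC difference 50 | 50% | 62.5 | 35 | 0.84 |
| FLC difference 50 | 90% | 62.5 | 15 | 2.06 |
| Plasmacytoma, size 1 | 50% | 1.25 | 0.625 | 1.00 |
| Any marker | none | same | same | 0 |

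**Serum.** From 3.0 g/dL, the baseline threshold is max(3.75, 3.5) = 3.75. After a fall to 1.5, the lowest-value threshold is max(1.875, 2.0) = 2.0, so the delay is log2(3.75/2.0) = 0.91. After a fall to 0.3 it is max(0.375, 0.8) = 0.8, giving 2.23. These delays apply only if footnote g is read from baseline; read from the lowest value, the delay is 0. For a starting value of 6 falling to 3 g/dL, the 1 g/dL rule alone gives 7 or 4 g/dL, depending on the reference.

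**Time.** The documents give no doubling time. For assumed values of 1, 3 and 6 months, the urine and FLC delays are:

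| Fall | 1 month | 3 months | 6 months |
|---|---|---|---|
| 50% (0.415 to 0.837 doublings) | 0.4 to 0.8 | 1.2 to 2.5 | 2.5 to 5.0 |
| 90% (0.862 to 2.059 doublings) | 0.9 to 2.1 | 2.6 to 6.2 | 5.2 to 12.4 |

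Markers are measured on day 1 of each cycle: every 21 days in induction (0.69 months) and every 28 days in maintenance (0.92 months). At the shortest doubling time, 0.42 months is below both intervals and 0.86 months is below the maintenance interval.

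**Who can be affected.** Section 11.6 expects 12 or more responders of 29 (12/29 = 41%). With minimal responders, this is the pool at risk, not the number affected. The number who progress first on a marker that had fallen is not given.

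**The case against.** The strongest reply is that lateness is relative. The text says baseline, and the documents nowhere require a lowest-value reference. They invoke the working group's uniform criteria, called modified in Section 11.1.1, but the cited source is not available here, so this may be the sponsor's deliberate choice. That stands. A reader might infer that the baseline rule breaks a required standard; the documents do not show it.

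A reader might also infer that serum progression is always dated late. That is not supported either. Footnote g hangs on a serum entry that sits under the baseline heading and may inherit that reference, which gives a delay. It may equally be an added route from the lowest value, which gives none. What is established is that the text permits both readings.

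A third tempting reading is that median PFS is overstated by a given number of months. Marker levels, depth of fall and doubling time are all assumed, and deaths, new lesions or hypercalcemia can end PFS first. No shift in the median can be estimated.

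Finally, Sections 3.1 and 6.3.2, which link the end of treatment to progression, do not now conflict with Appendix A. A difference would arise only if the endpoint rule changed.

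PFS is also a secondary, descriptive endpoint with no test or threshold attached, which limits the weight of the point but does not remove it.

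**Conclusion.** The point holds as a definition that should be improved, with medium confidence. For urine M-protein, the FLC difference (in its restricted group) and existing lesions, Appendix A as written lets a responder lose the whole response without a progression event on that marker. Relative to a lowest-value reference, the event is then dated later, never earlier. For serum it is dated later or inconsistently, depending on how footnote g is read.

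The size is 0.4 to 2.1 doublings in the urine and FLC examples, and 1.0 for a plasmacytoma that halved. For serum starting at 3.0 g/dL it is 0 to 0.91 after a 50% fall and 0 to 2.23 after a 90% fall. Any figure in months rests on an assumed doubling time, and the smallest delays would be lost within one visit interval. Patients with no reduction, and events from death, new lesions or hypercalcemia, are unaffected, as are the response rate and the Simon decision.

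**What to change.** Add to Section 11.6, for endpoint derivation only:

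> For PFS and duration of response, progression on serum M-protein, urine M-protein, FLC difference (only in patients without measurable serum and urine M-protein, as in Appendix A) and size of existing lesions or plasmacytomas is a rise of at least 25% from the lowest value recorded on study (baseline if there was no reduction). The Appendix A absolute minimum increases are measured from that same value, and footnote f applies. In footnote g the increases are measured from the lowest value, and the 5 g/dL condition refers to baseline. Reappearance of a plasmacytoma that had disappeared is counted as a new lesion.

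Use the same censoring date for PFS and duration of response. Report PFS by the present baseline reading as a sensitivity analysis. List separately any progression that rests only on the size of an existing lesion.

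The 5 g/dL condition is tied to baseline for a reason. Each threshold then rises with x, so the lowest-value threshold can never exceed the baseline one. A grid check (baseline 0.50 to 10.00 g/dL, lowest value 0 to baseline, step 0.01) gave a maximum difference of 0.00. Tied to the lowest value instead, a baseline of 5.0 and lowest value of 4.9 g/dL would give 6.125 against 6.0, a later date.

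**Cost.** One paragraph and a programming rule, with no new data: M-protein and FLC are measured on day 1 of every cycle and plasmacytomas every 2 cycles. Skeletal surveys are done only at baseline and progression, so for bone lesions the lowest value will usually be the baseline.

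**Downsides.** Reported PFS becomes somewhat shorter. The endpoint date can precede the date treatment stops. Small changes in a lesion may be noise, since there is no absolute minimum and the plasmacytoma modality is left to the treating physician.

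The missing start and end of duration of response is a separate gap to be filled. If the endpoint definition changes, the sponsor should reconcile it with Sections 3.1 and 6.3.2; no clinical rule is proposed here.
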